Randomization: We will stratify randomization by (1) severity of opiate use (COMM score) and (2) pain severity (BPI score). Urn randomization will be used to balance the randomization assignment with respect to these strata. The purpose of stratification is to distribute these potential prognostic factors equally across treatment groups.

Intent-to-Treat Analyses. All analyses will be performed on two samples: (1) the intent-to-treat sample consisting of all randomized subjects and (2) the completers sample consisting of all subjects who complete at least 7 out of 11 sessions.

Missing Data. We will perform attrition analyses on whether participants and dropouts differ on key variables (symptom severity) and whether variables on which they differ interact with treatments to affect outcome measures. As participants will be randomized to treatment, it is unlikely that missing data will produce biased estimates of treatment effect, as observed and unobserved covariates should theoretically be balanced across treatment groups. In addition, in general, less than 10% missing data have little impact upon study power and do not introduce bias, regardless of the missing data mechanism.⁷⁴ Larger proportions of data missing at random (MAR) or missing not at random (MNAR) could potentially bias study findings and reduce power. If the percent missing data are greater than 10%, propensity score methods will be used for data imputation. In the propensity score method, first the distribution of the missing indicator variable given the observed data is modeled to derive a propensity score. Then observations are grouped on these propensity scores and an approximate Bayesian bootstrap imputation is applied to each group.

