Time-Series Variables: The actigraphy devices will yield time-series data including sleep latency, total sleep time and sleep efficiency. Hierarchical Linear Modeling (HLM) will be applied to evaluate daily (time-series) pain, craving, opiate used, mood, anxiety, and physical activity ratings throughout the 3 phases of the study (baseline, treatment, and follow-up) and by group. The covariance structure of the model will be set to first-order autoregressive and independent effects of treatment on average daily pain will be assessed by controlling for daily fluctuations in craving, mood, anxiety, and activity in the model. Additional co-variates of CBT-related effects will include therapeutic alliance and pain coping styles. Additionally, cross-lag correlational analyses will be conducted on pain, craving, mood, anxiety, and activity data to estimate temporal order of changes during the trial.

Repeated Measures Variables: BPI, COMM, as well as mean weekly sleep latency, total sleep time and sleep efficiency scores will be examined with HLM using an unstructured covariance matrix. Subject-level intercepts will be entered into the model at level-1, and a time X group (real vs. sham tDCS) mixed model will be implemented. The primary model parameter of interest will be the time X group interaction term; however, main effects will be specified in the model. Effects of treatment on pain and opioid misuse will be separated from mood effects by co-varying mood and anxiety ratings at the individual subject-level.

Power: Effect sizes (Cohen's d) for CBT for chronic pain range from 0.3 to 1.4. A realistic effect-size estimate for the CBT intervention would be categorized as "medium/modest" (d=.5). The effect-size associated with clinical effects of tDCS on chronic pain in the current literature is also medium/modest (d=.5). With 150 subjects (75 in each group), power to detect effects (alpha=.05, effect-size d=.5, r among repeated measures=.5) is good to excellent (1- β = .80 and .99, respectively). Power will be higher for the HLM model as sources of intra-class variability are better managed.

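### The propensity-score bootstrap planned above 10% missing ignores person and day and leaves arm open; on the daily diary it weakens serial dependence and, depending on the donor pool, understates standard errors or dilutes the effect

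*Combined protocol and SAP*

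**What the plan says.** All references are to Statistical Analyses and Power in the combined protocol and SAP, unless another section is named.

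- **Missing Data** sets the trigger: "If the percent missing data are greater than 10%, propensity score methods will be used for data imputation". In the first step, "first the distribution of the missing indicator variable given the observed data is modeled to derive a propensity score". In the second, "Then observations are grouped on these propensity scores and an approximate Bayesian bootstrap imputation is applied to each group". The paragraph exempts no outcome. It does not give the donor unit (person or person-day), the role of arm, the number of classes, the number of imputations or a pooling rule.
- **Time-Series Variables** gives the diary model: "Hierarchical Linear Modeling (HLM) will be applied to evaluate daily (time-series) pain, craving, opiate used", over baseline, treatment and follow-up and by group. On dependence between days: "The covariance structure of the model will be set to first-order autoregressive". Cross-lag analyses of the same series follow.
- **Repeated Measures Variables** names subject-level intercepts and the time-by-group term, but for BPI, COMM and weekly sleep, not explicitly for the diary.
- **Hypotheses** 1a and 2a rest partly on diary pain, pain unpleasantness and craving. Primary Outcome Measures lists the diary as a primary pain measure.

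**The concern.** The score predicts whether a value is missing, not what it would have been. If missingness is unrelated to pain, the score carries no information on pain, so each fill is close to a random draw from its class. In a diary, most of what is known about a missed day lies in the same person's other days, above all the adjacent ones. The stated steps do not preserve that link. Each filled day pulls the person's series towards the class average and breaks the day-to-day chain.

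At stake are the validity or the size of the real-versus-sham comparison on a primary pain measure, and the serial dependence that the autoregressive and lead-lag analyses are meant to estimate. The rule would also replace something better: an HLM fitted by likelihood uses every observed day without imputation.

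**Working it through.** **The plan's own figure.** The plan gives no standard error, type I error or miss rate for the diary. The nearest figure is in Power, where 75 per arm, a .05 level, a standardised difference of 0.5 and a correlation of .5 between measures are said to give two power values, .80 and .99. For two means, d·√(n/2) = 0.5 × √37.5 = 3.06, so power ≈ Φ(3.06 - 1.96) = .86, not .80. The .99 reproduces as a within-between interaction. This mismatch is separate and does not bear on the present point.

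**Inputs from the documents.** 75 per arm (Power); 14 baseline days and 11 weekly sessions, so 11 × 7 = 77 treatment days (General Procedures).

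**Assumptions not in the documents.** Between-person share about .5 (varied .3-.7); day-to-day autocorrelation .3-.5; variance of person-specific change 0 or .2; 15% or 30% of days missing completely at random; five propensity classes; mostly five imputations with Rubin's rules. Each setting had 400-800 simulated trials, with Monte Carlo error near .01 on a rejection rate.

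**Step 1: who the donors are.** With five classes, an arm of 75 has 15 people per class, so a person's own days are about 1/15 = 7% of a within-arm pool. Pooled over 150 people, the share is 1/30 = 3%.

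**Step 2: variance and serial correlation.** A filled person mean is about (1-m) × own mean + m × class mean, so its variance falls by about (1-m)². A pair of adjacent days is intact with probability (1-m)², so lag-1 correlation falls similarly.

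| | Complete data | 15%: formula | 15%: simulated | 30%: formula | 30%: simulated |
|---|---|---|---|---|---|
| Between-person variance | .69 | .69 × .7225 = .50 | .52-.56 | .69 × .49 = .34 | .37-.45 |
| Lag-1 correlation | .71 | .71 × .7225 = .51 | .53-.56 | .71 × .49 = .35 | .38-.44 |

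The loss appears under every donor scheme.

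**Step 3: donors within arm, treatment-phase level.** The computed standard error shrinks by about (1-m). The true sampling SD does not, because the class mean carries the same people's sampling error. The expected ratio r of SE to true SD is therefore near .85 at 15% and .70 at 30%. Type I error is 2Φ(-1.96r): about .10 and .17.

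- Simulated r at 15%: .87-.93; type I error .07-.09.
- Simulated r at 30%: .72-.83; type I error .10-.18.

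Five imputations with Rubin's rules do not repair this.

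**Step 4: donors pooled across arms, arm not in the score.** Fills have the same expectation in both arms, so estimate, SD and SE all shrink together. A true 0.50 becomes 0.50 × .70 = 0.35 at 30%, and the simulations gave 0.35-0.36. The ratio r was 1.04-1.16 and type I error .025-.050 in one set of runs; over all runs the rate lay between .014 and .066. Coverage of the true 0.50 was 50-71%. With arm as one predictor in the score, results lay in between: at 30%, type I error .058-.100 and estimates 0.38-0.43.

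**Step 5: change from baseline.** Results depend on two further choices.

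- In one set of runs there was no inflation (.02-.06), but the effect was diluted. Dilution follows when classes mix baseline and treatment days, because the fills then have the same expectation in both phases.
- In another set, with within-arm donors and five imputations, type I error was .038-.064 at 15% and .060-.082 at 30%.
- The least favourable case had within-arm donors, phases not mixed (the estimate stayed at 0.50) and true change varying between people (variance .2). It gave .076-.081 at 15% and .105-.119 at 30%.

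**Step 6: observed days only.** Ratio .96-1.05, type I error .033-.068, and a true 0.50 estimated as 0.50.

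**The case against.** **The plan does not say that diary days will be imputed.** The paragraph opens with attrition and dropouts, and Compensation pays per diary with bonuses for completeness, so missingness may stay below 10%. This stands as a condition. But the trigger is automatic, no outcome is exempt, and 14 + 77 = 91 daily prompts before follow-up leave ample room to exceed it.

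**Standard errors that are too small are not a general result.** A reader might infer that the rule makes the diary tests anti-conservative whatever the details. The documents do not support that. They never confine donors to the arm, and pooled donors give near-nominal error with a diluted effect. A level-only test is also not obviously the planned one, since Hypothesis 1a speaks of improvement. With a random intercept plus AR(1) and no person-specific change, the ratio was .96-1.02 at 15% and .82-1.09 at 30%, often near nominal. This objection stands, and it limits the point.

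**If the diary model is AR(1) without a person effect, imputation is not the main problem.** The ratio is then already .35 with complete data. Agreed; that is a separate matter.

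**The score might include a person's own earlier ratings.** The text allows this, and it would soften the loss. But grouping on a missingness score still does not tie a fill to the person or the neighbouring day.

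**Conclusion.** The point holds in a conditional form. If the stated rule is applied to the diary, between-person variance and serial correlation are lost even under missingness completely at random, and the autoregressive and lead-lag analyses are distorted.

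For the arm comparison, the unspecified donor pool decides the harm:

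- **Within arm, treatment-phase level:** standard errors roughly 7-15% too small at 15% missing and 16-30% too small at 30%.
- **Pooled across arms:** error near nominal, effect reduced by about the missing fraction.
- **Change from baseline:** inflation small or absent in most settings, reaching about .12 at 30% in the least favourable one; the effect is diluted where phases are mixed.

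The sizes rest on an assumed between-person share, autocorrelation and miss rate, and arise only above 10% missing. No single type I error should be quoted as the expected rate for this trial. The text also does not state that fills come from other people; that follows from the small share of own days under the assumed classes. This should be fixed, but the documents do not establish that the primary test is invalid.

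**What to change.** In Missing Data and Time-Series Variables, state that the primary diary analysis is the HLM fitted by restricted maximum likelihood to all observed days, with no imputation at any missing rate. It is valid when missingness is at random given the modelled data. Delete the propensity-score bootstrap for the diary series.

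If imputation is kept as a sensitivity analysis, use two-level multiple imputation separately by arm, with a person effect and the person's neighbouring days, and state the number of imputations and pooling by Rubin's rules.

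The same likelihood approach suits the weekly HLMs, but no weekly data were simulated, so that extension rests on the general argument.

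The cost is wording, and less work than the stated method. Confidence intervals may be wider.

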Primary Outcome Measures: The primary measures are described in this section. Information regarding additional measures can be found in Table 1. (1) **Pain:** *Electronic Daily Diaries* will be administered using either standard feature or smart cell phones. The MUSC Technology Applications Center for Healthful Lifestyles (TACHL), directed by [name] (Co-I), will adapt software they originally configured for a daily monitoring protocol of PTSD symptoms. The pain/mood/craving/opiate-use questions will assess daily (via numeric rating scale; NRS) average pain, pain at its worst, pain unpleasantness, mood, activity-level, sleep quality, hours of sleep, opiate cravings, and will assess amount of prescription opiate. TACHL developed a SMS (Short Message Service)/MMS (Multimedia Messaging Service) encrypted gateway which enables ecological momentary assessment of pain, craving, etc. This communication system was selected due to its flexibility and ready availability for use on all cell phone types and their carriers. Measures will be collected at random times during waking-hours each day to minimize response bias associated with event-related reporting. See the Facilities and Resources section for more information on TACHL. The *Brief Pain Inventory (BPI)* is a widely used, 17-item self-report measure that assesses pain intensity and interference. Patients rate pain severity as well as the degree to which pain interferes with seven aspects of life: Work, Activity, Mood, Enjoyment, Sleep, Walking, and Relationships. (2) **Opiate Use Severity:** The *Current Opioid Misuse Measure (COMM)*^{68, 69} is a brief, 17-item measure designed to monitor chronic pain patients on opioid therapy. It assesses medication misuse behaviors such as, obtaining additional opiates from other doctors or the emergency room; taking medication that belongs to someone else; taking more opiates than prescribed; using opiates for alternative reasons (e.g., to reduce anxiety); consuming opiate medication via alternative route

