fMRI power to detect effects for planned contrasts was estimated as function of N, mean difference in percent signal change between block/conditions (μ_D), within-subject variability over time (σ_W), and between subject variability (σ_B) based on previous work conducted by our group. The effect size for our previously employed pain minus rest contrast was 1.8. Thus, power (1- β) reaches .80 with only 12 participants per group (two-tailed, alpha=.01). The present study is therefore well-powered to identify significant connectivity and activation patterns using the pain-rest block paradigm and functional connectivity methods proposed.

Hypotheses: The hypotheses and statistical approaches for testing each hypothesis is as follows:

Hypothesis 1a: CBT + real tDCS will result in significantly greater improvements, as compared to CBT + sham tDCS, in average daily pain (electronic diary), pain unpleasantness (electronic diary) and functional impairment due to pain (BPI). To test this hypothesis, time-series analysis of diary average pain and pain-unpleasantness ratings will be conducted and BPI total scores will be used as repeated measures variables using the HLM methods and model co-variate strategies delineated above.

Hypothesis 1b: CBT + real tDCS will result in significantly greater improvement, as compared to CBT + sham tDCS, in sleep latency, total sleep time and sleep efficiency. To test this hypothesis, time-series analysis of actigraphy sleep latency, total sleep time and sleep efficiency values will be used as repeated measures variables using the HLM methods and model co-variate strategies delineated above.

Hypothesis 1c: Sleep latency, total sleep time, and sleep efficiency will improve significantly after the manualized CBT module devoted to sleep hygiene compared to other CBT modules. To test this hypothesis, interrupted time-series analysis (via HLM) will be conducted with the "Sleep Hygiene" CBT module established as the temporal demarcation point.

Hypothesis 1d: Time-series data representing sleep latency, total sleep time and sleep efficiency *improvements will lead* any observed *improvements* in pain and functioning consistent with emerging data on the temporal relationship between sleep and pain.⁷⁹ To test this hypothesis, lead-lag analysis of key time-series variables (sleep latency, total sleep time and sleep efficiency, pain and functional impairment due to pain) will be conducted.

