Hypothesis 2a: CBT + real tDCS will result in significantly greater reductions, as compared to CBT + sham tDCS, in COMM scores and opiate craving ratings (electronic diary) compared to CBT + sham tDCS. To test this hypothesis, time-series analysis of diary ratings of opiate cravings will be conducted and COMM total scores will be used as repeated measures variables using the HLM methods and co-variate strategies delineated above.

Hypothesis 2b: CBT + real tDCS will result in significantly greater reductions, as compared to CBT + sham tDCS, in depression (BDI-II), anxiety (BAI), PTSD (PCL-M) and sleep (PSQI). To test this hypothesis, total scores on the identified measurements will be used as repeated measures variables using the HLM methods and co-variate strategies delineated above.

Hypothesis 2c: Total sleep time will mediate the clinical benefits of combined CBT-tDCS on chronic pain. To test this, structural equation modeling (SEM) will be used to examine the amount of variance explained in clinical improvement related to tDCS+CBT with and without total sleep time entered into the temporally dynamic model.

Hypothesis 3a: At baseline, percent BOLD signal change in the left DLPFC during pain blocks will be inversely related to BOLD signal in the left insula, ACC, thalamus, caudate, putamen, and medial prefrontal cortex.

Hypothesis 3b: After treatment, percent BOLD signal change in the left DLPFC during pain blocks will be significantly greater in the CBT + real tDCS group as compared to CBT + sham tDCS.

Hypothesis 3c: Functional connectivity between the left DLPFC and insula and ACC after treatment will be greater in participants who receive CBT + real tDCS as compared to CBT + sham tDCS.

Hypothesis 3d: The change in functional connectivity will be correlated with changes in pain (BPI), opiate use severity (COMM), and total sleep time.

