The risks associated with tDCS are minimal. There is no documented risk of seizure associated with tDCS, but participants with a history of seizure disorder will be excluded to ensure optimum safety. Side effects associated with tDCS include mild headache, tingling, itching, or stinging under the electrodes, and skin irritation.

After each therapy session, a vitamin-E/loe cream will be applied to the skin under the electrodes to reduce risks associated with skin drying. The Investigators have conducted over 800 tDCS sessions with no adverse or serious adverse events.

The risks associated with Actigraphy monitoring are minimal. Some mild skin irritation or allergic contact dermatitis can occur from wearing the actigraphy device. If the investigators detect any evidence of development of skin irritation in response to the device, its use will be discontinued.

Safety and Monitoring Plan

As discussed above, every attempt will be made to engage subjects for the duration of the 11-session treatment phase. Subjects will be considered drop-outs from the treatment phase if they fail to attend therapy sessions for three consecutive weeks, in spite of attempts by phone, email and mail to engage the subject in treatment. If at any point during the assessment, treatment or follow-up period, subjects are in need of medical management, psychiatric consultation or psychiatric hospitalization, they will be evaluated and referral or treatment will be provided as indicated. If a subject becomes suicidal, emergency psychiatric assessment will be arranged. The subject will be closely monitored clinically until they are no longer suicidal or an appropriate care plan is in place.

A procedure for clinical deterioration has been established based upon our experience with previous studies. Therapists will be instructed to use their best clinical judgment regarding emergencies and inform the PIs as soon as possible. In addition to relying on clinical judgment on the part of the treating therapists who are experienced with this population, we will also monitor the following weekly: pain, depression, anxiety, substance use, and PTSD symptoms using standardized measures (BPI, BDI, BAI, TLFB, PCL-M, COMM, breathalyzer tests, and urine drug screens) in order to detect any symptom worsening requiring further evaluation. Additionally, subjects will be advised to observe any signs of worsening pain, substance use or depression and to discuss these with their study therapist.

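### The model stated for Hypothesis 1a on average daily pain adjusts for daily variables that tDCS may itself change, so its contrast need not be the total effect that the hypothesis claims

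*Combined protocol and SAP*

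**What the plan says.** Under Statistical Analyses and Power, the Time-Series Variables paragraph applies hierarchical linear modelling to the daily ratings "throughout the 3 phases of the study (baseline, treatment, and follow-up) and by group". It then says that "independent effects of treatment on average daily pain will be assessed by controlling for daily fluctuations in craving, mood, anxiety, and activity". Hypothesis 1a claims greater improvement with real than with sham tDCS in diary average pain, diary unpleasantness and BPI function, and is tested "using the HLM methods and model co-variate strategies delineated above".

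The Repeated Measures Variables paragraph says that effects on pain and opioid misuse will be "separated from mood effects by co-varying mood and anxiety ratings at the individual subject-level". It names time by group as the parameter of interest. The daily model has no such statement.

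Three other places bear on the covariates:
- **Hypothesis 2a** predicts greater reductions with real tDCS "in COMM scores and opiate craving ratings (electronic diary".
- **Hypothesis 2b** predicts greater reductions in depression on the BDI-II and anxiety on the BAI, among others.
- **Primary Outcome Measures** lists the diary items as "average pain, pain at its worst, pain unpleasantness, mood, activity-level, sleep quality, hours of sleep, opiate cravings", plus the amount of prescription opiate taken. Craving, mood and activity are therefore rated daily alongside pain, after treatment starts as well as before. The list has no anxiety item.

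**The concern.** Randomisation protects the comparison of pain between the arms as randomised. That protection is lost once the model holds fixed something measured after treatment starts that treatment may have changed. If tDCS relieves pain partly by lowering craving or improving mood, adjusting for daily craving and mood removes that part. The result then answers whether tDCS helps pain by some other route.

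The plan's own hypotheses make this more than a theoretical worry, but the evidence is uneven across the four covariates. Craving is the only one that is the same measure as a hypothesised outcome. For mood and anxiety the link is by construct, because Hypothesis 2b names the BDI-II and BAI and not diary ratings. No hypothesis concerns activity.

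Pain is a primary outcome. A real benefit could be reported as weak or absent, and a benefit confined to mood could look like harm to pain.

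**Working it through.** **The plan's own figure.** The Power paragraph states 0.80 and 0.99 for 75 per group, d = 0.5, alpha 0.05 and r = 0.5. A two-sided two-sample t-test with those inputs gives 0.86, so 0.80 is not reproduced. The point does not depend on it; 0.86 is the unadjusted reference below.

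**Inputs.** From the plan: 75 per arm, alpha 0.05 (taken as two-sided), true pain effect 0.50 SD (the planning d). Assumed, with no source in the documents: tDCS improves the covariate (mood, as an example) by a = 0.3 or 0.5 SD; residual pain-mood correlation rho = 0.3, 0.5 or 0.7.

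**Single occasion.** Let pain = total effect × group + e and mood = a × group + u, with corr(e, u) = rho. Adjusting for mood gives:
- expected estimate = total − a × rho
- SE = √[(1 − rho²) × (2/75) × (1 + a²/4)]

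For a = 0.3 and rho = 0.5: 0.50 − 0.15 = 0.35; SE = √[0.75 × 0.02667 × 1.0225] = 0.143; power 0.68. With no true pain effect the expected estimate is −0.15, towards sham.

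| a | rho | Adjusted estimate (true 0.50) | Power (0.86 unadjusted) | Rejection if true effect is 0 |
|---|---|---|---|---|
| 0.3 | 0.3 | 0.41 | 0.73 | 0.09 |
| 0.3 | 0.5 | 0.35 | 0.68 | 0.18 |
| 0.3 | 0.7 | 0.29 | 0.69 | 0.42 |
| 0.5 | 0.3 | 0.35 | 0.58 | 0.15 |
| 0.5 | 0.5 | 0.25 | 0.40 | 0.40 |
| 0.5 | 0.7 | 0.15 | 0.24 | 0.82 |

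With no true effect, nearly all rejections favour sham. With a = 0 the estimate stays at 0.50 and power rises to 0.89, 0.94 and 0.99.

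**Daily three-phase model.** Simulation with 14 baseline, 77 treatment and 180 follow-up days (30 + 60 + 90; counts from the Compensation section) and first-order autoregressive errors gives, for the treatment-phase by group term:
- *Raw daily mood:* 0.15-0.41 SD, the same as the formula.
- *Centred on the person mean:* within 0.001 of raw. A person's mean is constant over time, so subtracting it leaves the change from baseline to treatment in the covariate.
- *Baseline values only:* 0.50-0.51. A value constant over time cannot alter a time-by-group term in a balanced design; the same holds for any single value per subject.
- *Centred within person and phase:* 0.50-0.51 when the effect is a step between phases. When the effect builds up during treatment, checks gave about 0.26-0.47 against 0.50, depending on the set-up, so this centring is only a partial safeguard.

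**Sensitivity to the day-level correlation.** The bias follows mainly the correlation between daily pain and daily mood. At 0.1 the formula gives 0.50 − 0.3 × 0.1 = 0.47 and 0.50 − 0.5 × 0.1 = 0.45; simulation gives about 0.46. At 0.2 the formula gives 0.44 and 0.40.

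**Direction of causation.** In a second simulation with a true effect of −1.00, covariates carrying 25% or 50% of it gave about −0.75 or −0.50 after raw adjustment. When pain drove the covariate instead, the adjusted estimate was −0.80, so the distortion does not require mood to cause pain.

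**BPI and COMM.** The Safety and Monitoring Plan says "we will also monitor the following weekly: pain, depression, anxiety, substance use, and PTSD symptoms using standardized measures", including the BDI and BAI, so weekly values exist. A weekly model (12 occasions, linear divergence to 0.5 SD) gives 0.15-0.41 with time-varying mood and 0.49-0.51 with one value per subject. The plan does not say which is meant.

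**The case against.** The plan openly aims at an independent effect, so the adjustment is deliberate. The Time-Series paragraph can also be read as a base model by phase and group, followed by an adjusted one. The first point stands as a description, but it leaves the total effect in Hypothesis 1a without a clearly assigned test. The second reading is possible but weak: the adjustment clause places the covariates inside the model, and Hypothesis 1a is tied to the covariate strategies. Hypothesis 2c does not fill the gap, because its mediator is total sleep time only.

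The size rests on assumptions. This stands in full: the documents give neither a mood effect nor a correlation, the lower end of 0.15 SD needs a strong daily correlation and a mood benefit as large as the pain benefit, and every figure models mood although craving has the firmest textual link.

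A reader might infer more than the documents support:
- *That all four covariates are predicted to respond to tDCS.* Only diary craving is named as such. Mood and anxiety are linked by construct, the source of a daily anxiety rating is not given in the diary list, and activity is in no hypothesis.
- *That BPI and COMM are equally affected.* The phrase about subject level may mean one value per person, which leaves the time-by-group term intact.
- *That the adjustment could manufacture a finding of efficacy.* When tDCS improves covariates that move with pain, as the hypotheses expect, the bias runs towards sham.

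**Conclusion.** The point holds for average daily pain. As written, the Hypothesis 1a contrast conditions on variables measured after randomisation, at least one of which the plan expects treatment to change. Unless those covariates enter as baseline or single values, the contrast is an effect net of their pathways. The plan states neither form.

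The size is illustrative: 0.15-0.41 SD in place of 0.50 SD under a mood effect of 0.3-0.5 SD and a correlation of 0.3-0.7, about 0.46 SD with a day-level correlation of 0.1, and no bias if tDCS leaves the covariates unchanged. The main risk is understating benefit or a false difference in favour of sham. For BPI and COMM the point is conditional on mood and anxiety entering as weekly time-varying ratings.

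**What to change.** In the Time-Series Variables paragraph and under Hypothesis 1a, state that the confirmatory model for average daily pain contains no covariate measured after the first tDCS session: either none, or pre-treatment values such as baseline COMM and BPI. Keep the model with daily craving, mood, anxiety and activity as a labelled secondary direct-effect or mediation analysis, and give the source, timing and centring of each covariate there.

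In the Repeated Measures Variables paragraph, state that mood and anxiety enter the confirmatory BPI and COMM models only as pre-treatment values.

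The cost is wording and one extra model, with no new data. If tDCS does not move mood, some precision is given up: single-occasion power of 0.86 instead of 0.89-0.99 under the assumptions above.
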